2.2 RESEARCH ELIGIBILITY EVALUATION

Blood tests (except serologies) and pregnancy test to be done within one week of study entry, other studies to be done within 4 weeks before study entry:

- Complete History and Physical examination.
- CBC, differential, PT, PTT, SGOT, SGPT, LDH, alkaline phosphatase, bilirubin, albumin, calcium, phosphate, uric acid, creatinine (24 hour creatinine clearance if serum creatinine > 1.5 mg/dL), electrolytes, urinalysis, HIV serology, hepatitis B surface antigen and Anti Hepatitis B core antibody.
- Unilateral bone marrow aspirate and biopsy if not performed within 1 month.
- HCG (urine) in women of childbearing potential.
- Electrocardiogram.
- Staging: CT scans of chest, abdomen and pelvis.
- PET as clinically indicated.
- Head CT or Brain MRI and lumbar puncture with flow and cytology as clinically indicated.

2.3 PATIENT REGISTRATION

Authorized staff must register an eligible candidate with NCI Central Registration Office (CRO) within 24 hours of signing consent. A registration Eligibility Checklist from the web site (<http://camp.nci.nih.gov/CCR/welcome.htm>) must be completed and faxed to [contact]. After confirmation of eligibility at Central Registration Office, CRO staff will call pharmacy to advise them of the acceptance of the patient on the protocol prior to the release of any investigational agents. Verification of Registration will be forwarded electronically via e-mail to the research team. A recorder is available during non-working hours.

3 STUDY IMPLEMENTATION

3.1 STUDY DESIGN:

3.1.1 Phase I Design

There will be 3-4 defined dose levels, with 3-6 patients treated at each dose level. The Phase I dose escalation will follow one of two different escalation rates shown in Tables 1 and 2. If DLT is observed in 0-1/6 patients on dose level 1, escalation will proceed according to Table 1. If DLT is observed in 2 of up to 6 patients on dose level 1, escalation will proceed according to Table 2. Escalation decision rules are shown below:

Number of Patients with DLT at a Given Dose Level	Escalation Decision Rule
0 out of 3	Enter 3 patients at the next dose level
≥ 2	Dose escalation will be stopped. This dose level will be declared the maximally administered dose (highest dose administered). Three (3) additional patients will be entered at the next lowest dose level if only 3 patients were treated previously at that dose.

1 out of 3	Enter at least 3 more patients at this dose level. 
• If 0 of these 3 patients experience DLT, proceed to the next dose level.• If 1 or more of this group suffer DLT, then dose escalation is stopped, and this dose is declared the maximally administered dose. Three (3) additional patients will be entered at the next lowest dose level if only 3 patients were treated previously at that dose. This rule does not apply to dose level one. Please see section 4.2
≤1 out of 6 at highest dose level below the maximally administered dose	This is the recommended phase 2 dose. At least 6 patients must be entered at the recommended phase 2 dose.

Entry onto a new dose level cannot occur until all patients on the previous dose level have completed cycle 1. The PI or his designee must be consulted regarding the proper dose level for all new patients. The definition of DLT is described in section 4.2.

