3.2 DRUG ADMINISTRATION

3.2.1 Phase 1 Dosing and Schedule

The Phase I dose escalation will follow one of two different escalation rates shown in Tables 1 and 2 below. If DLT is observed in 0/3 or 1/6 patients on dose level 1, subsequent patients will be enrolled according to the paradigm described in Table 1 below. If DLT is observed in 2/6 patients on dose level 1, subsequent patients will be enrolled according to the paradigm described in Table 2 below.

Flavopiridol dose levels

Table 1	Cycle 1, Week 1		Cycle 1, Weeks 2–4, AND All weeks During All Subsequent Cycles	
Dose level	Bolus x30 minutes IV	Continuous infusion x 4 hrs	Bolus x30 minutes IV	Continuous infusion x 4 hrs
1	30mg/m ²	30mg/m ²	30mg/m ²	50mg/m ²
2	30mg/m ²	50mg/m ²	30mg/m ²	50mg/m ²
3	30mg/m ²	50mg/m ²	40mg/m ²	60mg/m ²
4	40mg/m ²	60mg/m ²	40mg/m ²	60mg/m ²

Table 2	Cycle 1, Week 1	Cycle 1, Weeks 2–4, AND All weeks During All Subsequent Cycles

Dose level	Bolus x30 minutes IV	Continuous infusion x 4 hrs	Bolus x30 minutes IV	Continuous infusion x 4 hrs
1	30mg/m ²	30mg/m ²	30mg/m ²	50mg/m ²
1A	25mg/m ²	25mg/m ²	30mg/m ²	50mg/m ²
1B	25mg/m ²	25mg/m ²	40mg/m ²	60mg/m ²

- Administer weekly x 4 consecutive weeks, followed by 2 weeks without flavopiridol treatment for a cycle duration of 6 weeks (1 cycle).
- For cycles 2-6, administer the doses given during cycle 1, weeks 2-4 for all doses.
- Administer up to 6 cycles if no disease progression.
- Restage all positive sites of disease after every 2 cycles, except bone marrow which should be repeated after other sites have achieved a CR.
- Administer flavopiridol in the inpatient unit on cycle 1, dose 1 (bolus and infusion).
- Unless medically contraindicated, all patients will receive allopurinol 300 mg per day on cycle 1 x 5 days. All patients should receive at least 200 mL/hr 0.9% Sodium Chloride Injection for 6 hours prior to the first flavopiridol dose. Detailed required guidelines for Tumor Lysis Syndrome prevention is shown in section 4.3.
- If cycle 1, dose 1 is tolerated without TLS, subsequent doses may be administered outpatient.

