- For patients who develop grade 4 neutropenia, G-CSF at a dose of 300 mcg/day SC will be instituted. Flavopiridol can be administered when the ANC is above 500. If grade 4 neutropenia persists for more than 7 days on G-CSF this will constitute a DLT and warrant a dose reduction in drug by 20%. Once G-CSF is instituted, it will be continued as prophylaxis from day 2 through day 6 of each week of treatment. G-CSF should be stopped the day prior to each flavopiridol dose.

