3.2.2 Phase 2 Dosing

- Dose will be the MTD from the phase I portion.
- Administer weekly x 4 consecutive weeks, followed by 2 weeks without flavopiridol treatment for a cycle duration of 6 weeks (1 cycle).
- For all weeks of all cycles after cycle 1, patients will receive the dose administered on cycle 1, weeks 2-4.
- Administer up to 6 cycles if no disease progression.
- Restage all positive sites of disease after every 2 cycles, except bone marrow which should be repeated after other sites have achieved a CR.

3.2.3 Definition of Dose Limiting Toxicity:

Dose-limiting toxicity will be determined during the first cycle of treatment and is defined as:

- any grade 3 or greater non-hematologic toxicity excluding transient liver function abnormalities that resolve spontaneously within 10 days and/or transient electrolyte abnormalities that are not life-threatening, or fatigue
- grade 4 thrombocytopenia (< 25,000/mcL) persisting for 4 or more days

- grade 4 neutropenia ANC < 500/mcL persisting for 7 or more days despite the institution of G-CSF
- inability to continue with cycle 2 by 3 weeks after the end of cycle 1. Exceptions to this (i.e. accidents, family emergencies, etc) will be evaluated on a case-by-case basis.
- irreversible \geq grade 2 non-hematologic toxicity
- irreversible grade 3 thrombocytopenia at least possibly due to flavopiridol.
- And is a drug related event with an attribution of possible, probable or definite.

Patients with compromised bone marrow function from lymphoma will not be evaluable for hematologic related DLT. Irreversible is defined as lasting > 3 weeks. All toxicity will be evaluated and scored using NCI Common Terminology Criteria for Adverse Events (CTCAE) version 3.0 until December 31, 2010. CTCAE version 4.0 will be utilized beginning January 1, 2011.

3.3 TREATMENT MODIFICATIONS:

Patients should have recovered toxicities that are clinically significant and attributable to flavopiridol to grade 1 or baseline before beginning another cycle. If toxicity has not resolved to this level within 3 weeks from the end of the previous cycle, flavopiridol will be discontinued.

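### The next dose level can open when cycle 1 ends (day 42), but three DLT criteria may not be scorable until about day 63, and no rule covers a patient still pending

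*Combined protocol and SAP*

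**What the plan says.** All references are to the combined protocol and SAP.

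- **Escalation gate (3.1.1):** "Entry onto a new dose level cannot occur until all patients on the previous dose level have completed cycle 1". The same section adds: "The PI or his designee must be consulted regarding the proper dose level for all new patients".
- **Cycle length (3.2.1):** four weekly doses and then two weeks off, 6 weeks in all.
- **DLT window (3.2.3):** "Dose-limiting toxicity will be determined during the first cycle of treatment and is defined as", followed by the list of criteria.
- **Criteria that depend on a 3-week period (3.2.3):** one is "inability to continue with cycle 2 by 3 weeks after the end of cycle 1". Two others are irreversible non-hematologic toxicity of grade 2 or higher and irreversible grade 3 thrombocytopenia, where "Irreversible is defined as lasting > 3 weeks".
- **Recovery before the next cycle (3.3):** "If toxicity has not resolved to this level within 3 weeks from the end of the previous cycle, flavopiridol will be discontinued".
- **Counting rule (3.1.1 and 6):** escalate on 0 of 3 or 1 of 6. The MTD is the highest level with 0 or 1 DLT in 6. Neither section mentions assessments that are still open.
- **Neutropenia threshold:** 3.2.1 says "If grade 4 neutropenia persists for more than 7 days on G-CSF this will constitute a DLT". Section 3.2.3 and the dose-reduction rule in 3.3.1 both set the limit at 7 days or more.

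**The concern.** The escalation gate and the DLT definition run on different clocks. The gate closes the observation period at the end of cycle 1, while three of the listed DLTs can need up to three more weeks to establish. A patient with unresolved toxicity or a delayed cycle 2 at day 42 is neither a DLT nor a confirmed non-DLT, and the plan does not say which to assume or whether to wait.

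Two things are at stake.

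- **Safety.** Following the text, up to three patients can start the next level before a DLT at the level below is known. This matters most from level 2 to 3 (Table 1) and from 1A to 1B (Table 2), where the repeated weekly dose rises. Level 1 also matters: a second DLT in six sends later patients to Table 2, so a second DLT confirmed after the gate could leave them on Table 1.
- **The MTD.** Limiting DLT to the first cycle can be read as excluding one confirmed on, say, day 50, although the criterion list plainly includes such events. Two investigators could score the same patient differently, and the MTD sets the phase II dose.

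**Working it through.** **Timing.** Inputs are from 3.1.1, 3.2.1 and 3.2.3.

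- Cycle length: (4 + 2) × 7 = 42 days, which reproduces the stated 6 weeks. Doses fall on days 1, 8, 15 and 22. The gate is day 42.
- Cycle-2 criterion: decided by 42 + 21 = day 63.
- Irreversible criteria: reached at about onset day + 21.

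| Onset day | Reaches 3 weeks at about | Known by day 42? |
|---|---|---|
| 15 | day 36 | yes |
| 21 | day 42 | borderline |
| 22 (dose 4) | day 43 | no |
| 29 | day 50 | no |
| 36 | day 57 | no |
| 42 | day 63 | no |

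Persistent toxicity that starts at or after dose 4 therefore cannot be classed as irreversible at the gate. Section 6 equates 16 weeks with 4 cycles, which would imply a 28-day cycle. On that reading the two dates are days 28 and 49, with the same 21-day gap.

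**Dose steps** (Tables 1 and 2, bolus + infusion, mg/m²).

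- Weekly dose after week 1: levels 1, 2 and 1A, 30 + 50 = 80; levels 3, 4 and 1B, 40 + 60 = 100. The increase is 20/80 = 25%.
- Levels 1 to 2 and 3 to 4 change only the week 1 dose.
- Routing from level 1: the week 1 dose is 25 + 25 = 50 at 1A and 30 + 50 = 80 at level 2.

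**Chance that the next level opens.** The documents give neither the share of DLTs that are late nor the number of patients pending, so both are assumed. Let p be the true DLT risk, L the late share, v = p(1 − L), and m the number of patients pending in each cohort of three. The first three patients are taken as fully scored by the second gate.

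- No DLT visible at the gate: P0 = (1 − p)^(3−m) × (1 − v)^m
- One DLT visible at the first gate, and no late one by the second: P1 = ((3 − m)p + mv) × (1 − p)²
- P(open) = P0 + P1 × P0

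Full scoring, p = 0.33: P0 = 0.67³ = 0.3008; P1 = 3 × 0.33 × 0.67² = 0.4444; P(open) = 0.3008 + 0.4444 × 0.3008 = 0.434.

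One pending, 10% late: v = 0.297; P0 = 0.67² × 0.703 = 0.3156; P1 = 0.957 × 0.4489 = 0.4296; P(open) = 0.451.

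| p | Late share | Full scoring | m = 1 | m = 2 | m = 3 |
|---|---|---|---|---|---|
| 0.33 | 10% | 0.434 | 0.451 | 0.468 | 0.486 |
| 0.33 | one third | 0.434 | 0.488 | 0.549 | 0.615 |
| 0.40 | 10% | 0.309 | 0.327 | 0.345 | 0.364 |
| 0.40 | 25% | 0.309 | 0.352 | 0.400 | 0.454 |

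If late DLTs are never counted, v replaces p throughout: P(open) = (1 − v)³ + 3v(1 − v)⁵. At p = 0.33 this gives 0.50 with 10% late and 0.61 with 25% late. At p = 0.40 it gives 0.38 and 0.49.

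**Neutropenia.** An episode of exactly 7 days on G-CSF is a DLT under 3.2.3 and not one under 3.2.1.

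**The case against.** The dates are not in dispute. The case on the other side concerns consequence and size.

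1. *Late DLTs can still be counted.* The decision table in 3.1.1 and the MTD definition in section 6 carry no time limit, and reading the first-cycle phrase as a cut-off would void a listed criterion. This stands in part. A sensible investigator would count a late DLT, and any effect on the MTD then arises mainly in the final cohort. The text does not require it, however, and later counting does not undo entry to the higher dose.
2. *Pending patients are visible.* Section 3.3 calls for recovery to grade 1 or baseline before another cycle, 3.3.1 holds doses for low platelets, laboratory tests are weekly during therapy, and section 6.1 provides ongoing review by the investigator and CTEP. These lower the practical risk. None of them imposes a wait, and consulting the investigator on dose level does not either.
3. *Few events are affected.* Most non-hematologic toxicity of grade 3 or higher counts at once. What remains is mainly persistent grade 2 non-hematologic toxicity, persistent grade 3 thrombocytopenia and a delayed cycle 2. This is correct, and a late share of one quarter or one third has no support in the documents.
4. *Three pending patients is an extreme.* Section 6 expects up to 71 patients in up to 3 years, or 3 × 365/71 ≈ 15 days apart if accrual is even. When the third patient reaches day 42, the second is near day 57 and the first near day 73. That points to one or two pending, and to one or two entries at the next level during the 21-day gap. Phase I accrual could be faster or clustered, so three is a ceiling and not a typical value.
5. *The neutropenia mismatch is a separate matter.* Agreed. It affects only episodes of exactly 7 days and adds nothing to the weight of the gate problem.

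**Conclusion.** The concern holds and should be fixed. The timing conflict follows from the protocol's own definitions: a gate at day 42, one DLT criterion open to day 63, and two that cannot be met by day 42 when onset is at or after day 22. Applying the gate exactly as written allows a higher dose to start before a listed DLT at the level below can be scored. Acute criteria and early-onset toxicity are unaffected.

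The size is much less certain than the timing. With one or two patients pending and 10% of DLTs late, the chance of opening the next level rises by about 2 to 4 percentage points (43% to 45–47% at a true risk of 33%; 31% to 33–34% at 40%). The larger figures need a higher late share, three pending patients, or a reading under which late DLTs never count.

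**What to change.** Three wording changes:

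- **3.1.1:** open a new level only when every patient on the level below has finished cycle 1 and has either begun cycle 2 with no open toxicity that could still become a DLT, or been followed until each 3.2.3 criterion is settled. That is up to 3 weeks past the end of cycle 1, or longer if needed to show a duration of more than 3 weeks.
- **3.2.3:** define the window as toxicity that arises in cycle 1, followed through that same period, and state that late-confirmed DLTs enter the 0/3, 1/6 and final 0–1/6 counts.
- **3.2.1:** set the neutropenia DLT at 7 days or more, to agree with 3.2.3 and 3.3.1.

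If phase I enrolment is already complete, the same rules should govern how its DLTs are scored and reported.

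The cost is an amendment plus generally up to 3 weeks per escalation, and only when a patient has unresolved toxicity or a delayed cycle 2. With one wait per escalation, the three Table 1 steps add at most about 3 × 3 = 9 weeks; a level expanded to six patients could need a second wait. A patient who starts cycle 2 on time with nothing unresolved adds no delay.

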3.1.2 Phase 2 Design

The Phase 2 dose and schedule will be determined by the MTD in the Phase 1 portion. Please contact the PI or Study Chair for appropriate dose.

3.2 DRUG ADMINISTRATION

3.2.1 Phase 1 Dosing and Schedule

The Phase I dose escalation will follow one of two different escalation rates shown in Tables 1 and 2 below. If DLT is observed in 0/3 or 1/6 patients on dose level 1, subsequent patients will be enrolled according to the paradigm described in Table 1 below. If DLT is observed in 2/6 patients on dose level 1, subsequent patients will be enrolled according to the paradigm described in Table 2 below.

Flavopiridol dose levels

Table 1	Cycle 1, Week 1		Cycle 1, Weeks 2–4, AND All weeks During All Subsequent Cycles	
Dose level	Bolus x30 minutes IV	Continuous infusion x 4 hrs	Bolus x30 minutes IV	Continuous infusion x 4 hrs
1	30mg/m ²	30mg/m ²	30mg/m ²	50mg/m ²
2	30mg/m ²	50mg/m ²	30mg/m ²	50mg/m ²
3	30mg/m ²	50mg/m ²	40mg/m ²	60mg/m ²
4	40mg/m ²	60mg/m ²	40mg/m ²	60mg/m ²

Table 2	Cycle 1, Week 1	Cycle 1, Weeks 2–4, AND All weeks During All Subsequent Cycles

Dose level	Bolus x30 minutes IV	Continuous infusion x 4 hrs	Bolus x30 minutes IV	Continuous infusion x 4 hrs
1	30mg/m ²	30mg/m ²	30mg/m ²	50mg/m ²
1A	25mg/m ²	25mg/m ²	30mg/m ²	50mg/m ²
1B	25mg/m ²	25mg/m ²	40mg/m ²	60mg/m ²

- Administer weekly x 4 consecutive weeks, followed by 2 weeks without flavopiridol treatment for a cycle duration of 6 weeks (1 cycle).
- For cycles 2-6, administer the doses given during cycle 1, weeks 2-4 for all doses.
- Administer up to 6 cycles if no disease progression.
- Restage all positive sites of disease after every 2 cycles, except bone marrow which should be repeated after other sites have achieved a CR.
- Administer flavopiridol in the inpatient unit on cycle 1, dose 1 (bolus and infusion).
- Unless medically contraindicated, all patients will receive allopurinol 300 mg per day on cycle 1 x 5 days. All patients should receive at least 200 mL/hr 0.9% Sodium Chloride Injection for 6 hours prior to the first flavopiridol dose. Detailed required guidelines for Tumor Lysis Syndrome prevention is shown in section 4.3.
- If cycle 1, dose 1 is tolerated without TLS, subsequent doses may be administered outpatient.
- For patients who develop grade 4 neutropenia, G-CSF at a dose of 300 mcg/day SC will be instituted. Flavopiridol can be administered when the ANC is above 500. If grade 4 neutropenia persists for more than 7 days on G-CSF this will constitute a DLT and warrant a dose reduction in drug by 20%. Once G-CSF is instituted, it will be continued as prophylaxis from day 2 through day 6 of each week of treatment. G-CSF should be stopped the day prior to each flavopiridol dose.

3.2.2 Phase 2 Dosing

- Dose will be the MTD from the phase I portion.
- Administer weekly x 4 consecutive weeks, followed by 2 weeks without flavopiridol treatment for a cycle duration of 6 weeks (1 cycle).
- For all weeks of all cycles after cycle 1, patients will receive the dose administered on cycle 1, weeks 2-4.
- Administer up to 6 cycles if no disease progression.
- Restage all positive sites of disease after every 2 cycles, except bone marrow which should be repeated after other sites have achieved a CR.

3.2.3 Definition of Dose Limiting Toxicity:

Dose-limiting toxicity will be determined during the first cycle of treatment and is defined as:

- any grade 3 or greater non-hematologic toxicity excluding transient liver function abnormalities that resolve spontaneously within 10 days and/or transient electrolyte abnormalities that are not life-threatening, or fatigue
- grade 4 thrombocytopenia (< 25,000/mcL) persisting for 4 or more days

- grade 4 neutropenia ANC < 500/mcL persisting for 7 or more days despite the institution of G-CSF
- inability to continue with cycle 2 by 3 weeks after the end of cycle 1. Exceptions to this (i.e. accidents, family emergencies, etc) will be evaluated on a case-by-case basis.
- irreversible \geq grade 2 non-hematologic toxicity
- irreversible grade 3 thrombocytopenia at least possibly due to flavopiridol.
- And is a drug related event with an attribution of possible, probable or definite.

Patients with compromised bone marrow function from lymphoma will not be evaluable for hematologic related DLT. Irreversible is defined as lasting > 3 weeks. All toxicity will be evaluated and scored using NCI Common Terminology Criteria for Adverse Events (CTCAE) version 3.0 until December 31, 2010. CTCAE version 4.0 will be utilized beginning January 1, 2011.

3.3 TREATMENT MODIFICATIONS:

Patients should have recovered toxicities that are clinically significant and attributable to flavopiridol to grade 1 or baseline before beginning another cycle. If toxicity has not resolved to this level within 3 weeks from the end of the previous cycle, flavopiridol will be discontinued.

3.3.1 Hematological Toxicity

Dose modifications of flavopiridol should be made according to the following schema:

Hematological toxicity on Day 1 of Cycle:

Platelets (at start of cycle)	Flavopiridol Dose
< 50,000	Delay up to 2 weeks until Plts \geq 50,000 and reduce dose 20%.
Neutrophil count (at start of cycle)	
< 500	Start G-CSF. Administer flavopiridol when ANC is > 500 . Once G-CSF is instituted, continue to administer it prophylactically for subsequent (days 2-6 each week) doses
< 500 despite G-CSF for 7 or more days	Reduce dose of flavopiridol by 20% and repeat dose only when ANC is > 500

Hematological Toxicity During the Cycle:

Platelets	Flavopiridol Dose
< 50,000	Delay up to 2 weeks until Plts \geq 50,000 and reduce dose 20%.
Neutrophil count	
< 500	Start G-CSF. Administer flavopiridol when ANC is > 500 . Once G-CSF is instituted, continue to administer it prophylactically for subsequent (days 2-6 each week) doses
< 500 for 7 or more days despite G-CSF	Reduce dose of flavopiridol by 20% and repeat dose only when ANC is > 500

If grade 4 neutropenia lasting for 7 or more days on G-CSF or grade 3 thrombocytopenia develops during treatment, hold the next dose until recovery below this toxicity and reduce dose by 20% for subsequent doses and cycles as instructed in above tables.

3.3.2 Diarrhea Toxicity

Diarrhea treatment during cycle: At first loose stool: Start loperamide 2 mg p.o. q 2 h while awake and q 4 h while sleeping. Continue around the clock until 12 h diarrhea free. If diarrhea free > 12 h, stop loperamide. Lomotil may also be given for diarrhea in addition to or as an alternative to loperamide. Please note the manufacturer's recommended maximum daily dose of loperamide is 16 mg. If grade 3 diarrhea or diarrhea is accompanied by mucus or dehydration, hold doses of flavopiridol (if applicable) and hydrate.

Diarrhea Toxicity on Previous Cycle:

Diarrhea on previous cycle	Flavopiridol dose
< Grade 3	No change
Grade 3 or associated with mucus or dehydration	Reduce dose by 20% on all subsequent cycles.
Grade 4	Hold until diarrhea grade < 3 and reduce dose 20%

Diarrhea Toxicity During the Cycle:

Diarrhea on previous week	Flavopiridol dose
< Grade 3	No change
Grade 3	Reduce dose by 20%. If toxicity persists for > 7 days after reduction, hold dose.
Grade 4	Hold until diarrhea grade < 3 and reduce dose 20%

If grade 3 diarrhea on previous cycle, reduce dose 20% on subsequent cycles. If grade 4 diarrhea on previous cycle, hold until diarrhea < grade 3 and reduce dose 20%.

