3.3.5 Liver Function Tests

Liver tests, including AST, ALT and total bilirubin will be checked weekly during therapy.

- In order to initiate a cycle, liver function tests must be at grade ≤ 2 .
- Within 24 hours prior to each dose, LFTs must be ≤ 2 in order for therapy to be administered.
- If liver function tests demonstrate \geq grade 3 elevation, flavopiridol will be held until resolution to ≤ 2 .
- If \geq grade 3 elevation occurred flavopiridol will be reduced by one dose level (except for patients at dose level 1 in which case flavopiridol will be discontinued).

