3.3.7 Other Clinically Significant (determined by PI or AI) Non-Hematological Toxicity

These are adverse events that are felt to be at least possibly related to flavopiridol administration and in the opinion of the PI or AI do not have serious medical consequences (i.e. replaced easily) such as low phosphorus, low albumin or low calcium.

Symptom grade	Management
≤ grade 2	Treat symptomatically
≥ grade 3	Hold next dose until grade 1 or baseline and resume flavopiridol if further therapy is indicated

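### Section 3.3.2 gives two dosing rules for diarrhea within a cycle: the narrative holds flavopiridol at grade 3 or with mucus or dehydration, while the within-cycle table reduces by 20% or makes no change

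*Combined protocol and SAP*

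**What the plan says.** Section 3.3.2 contains a narrative on treatment during the cycle and two tables.

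- **Narrative.** After the loperamide instructions it says: "If grade 3 diarrhea or diarrhea is accompanied by mucus or dehydration, hold doses of flavopiridol (if applicable) and hydrate".
- **Within-cycle table**, keyed to diarrhea in the previous week. Milder diarrhea than grade 3 leaves the dose as it is. At grade 3 the instruction is: "Reduce dose by 20%. If toxicity persists for > 7 days after reduction, hold dose". The row for grade 4 stops treatment until the diarrhea has improved to less than grade 3 and then cuts the dose by a fifth.
- **Previous-cycle table.** The row that triggers a 20% reduction is labelled "Grade 3 or associated with mucus or dehydration", so mucus or dehydration counts there as a trigger separate from grade 3.

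The opening of section 3.3 covers the start of a new cycle: "Patients should have recovered toxicities that are clinically significant and attributable to flavopiridol to grade 1 or baseline before beginning another cycle". The gap is therefore confined to the weekly doses within a cycle.

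**The concern.** The narrative and the within-cycle table govern the same decision, namely what to give at the next weekly dose, and neither is given precedence. They differ in two places. At grade 3 the narrative holds, while the table reduces and holds only later. Below grade 3 with mucus or dehydration the narrative holds, while the table leaves the dose unchanged.

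At stake are patient safety and consistent dosing in a trial that has toxicity as a primary objective (section 1.1.1). Read on its own, the table permits a dose during active grade 3 or dehydrating diarrhea. The rule is likely to be needed. Diarrhea is in the more-than-20% column of the adverse event list (section 8.4). It was dose limiting on the 72-hour schedule, and it is listed among the grade 3 or 4 toxicities seen with the hybrid schedule in CLL/SLL (section 1.2.3).

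**Working it through.** The plan gives no figure of its own on this point, so the check sets the rules side by side and works out the dose each one gives.

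**Step 1. Planned doses (section 3.2.1, Tables 1 and 2, bolus plus infusion, weeks 2–4 of cycle 1 and all later weeks).**

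| Dose levels | Planned dose, mg/m² | After a 20% cut, mg/m² |
|---|---|---|
| 1, 2, 1A | 30 + 50 = 80 | 0.8 × 80 = 64 |
| 3, 4, 1B | 40 + 60 = 100 | 0.8 × 100 = 80 |

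**Step 2. Dose given under each rule.**

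| State when the next weekly dose is due | Narrative | Within-cycle table |
|---|---|---|
| Grade 3 still present | 0 | 64 or 80 mg/m² |
| Grade 1–2 with mucus or dehydration | 0 | 80 or 100 mg/m² |
| Grade 1–2 without either, no grade 3 in the previous week | full dose | full dose |

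The two rules part only in the first two rows.

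**Step 3. Sensitivity to the base of the cut.** The protocol does not say which dose the 20% is taken from. This matters for cycle 1 dose 2, because the week 1 dose can differ from the weeks 2–4 dose. A cut from the week 1 dose would give:

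- level 1: 0.8 × 60 = 48 mg/m²
- levels 2 and 3: 0.8 × 80 = 64 mg/m²
- level 4: 0.8 × 100 = 80 mg/m²
- levels 1A and 1B: 0.8 × 50 = 40 mg/m²

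For that one dose the table's grade 3 row therefore gives between 40 and 80 mg/m², depending on level and base. The narrative still gives 0.

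**Step 4. Reach of the table.** It can apply to doses 2–4 of each cycle: 3 × 6 = 18 of 4 × 6 = 24 planned doses over six cycles. This counts the decisions it could govern, not the doses affected. The documents give no grade 3 diarrhea rate for this schedule, so the number affected cannot be computed.

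**Step 5. Can the two texts be read together?** One could hold while diarrhea is active and resume at 80%. The grade 3 row does not say so. Its only hold comes more than 7 days after a reduction, which with weekly dosing implies that at least one reduced dose has already been given while some toxicity continued. It has no restart threshold, although the grade 4 row has one. On the literal table, a patient who improves from grade 4 to grade 3 is still held, while a patient newly at grade 3 is dosed. No combined reading supplies the missing mucus and dehydration exception in the row below grade 3.

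**Step 6. Comparable rules in section 3.3.** For grade 3 thrombocytopenia, section 3.3.1 says "hold the next dose until recovery below this toxicity and reduce dose by 20% for subsequent doses and cycles". For liver tests at grade 3 or above, section 3.3.5 says "flavopiridol will be held until resolution to" grade 2 or lower. This is a pattern and not a universal rule: section 3.3.3 states no hold for a first clotting event.

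**Step 7. Effect on design quantities.** Under section 3.2.3, drug-related grade 3 diarrhea in cycle 1 is a DLT whichever dosing rule follows. The stage sizes and response cut-offs in section 6 do not depend on these rules.

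**The case against.** The best defence is that the two texts do different jobs. The narrative covers acute care, with holding only if applicable, and the table, headed by the previous week, sets the next dose once the episode has settled. On this view the grade 4 row needs its own hold because the narrative names only grade 3 and mucus or dehydration. The toxicity that persists after a reduction could also be residual diarrhea below grade 3.

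This reading is possible, and part of it stands. The 0 against 64 or 80 mg/m² contrast needs grade 3 to be present still on the dose day, a condition the table does not state. A reader might infer that the protocol requires dosing through grade 3 diarrhea, or that clinicians would diverge in every grade 3 case. The text supports only that such dosing is permitted if the table is followed alone. What does not stand is that the defence resolves the matter: the division of labour is nowhere stated, grade 3 is left without a restart threshold, and the mucus and dehydration gap remains.

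Two other stronger inferences should be resisted.

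- Section 3.3.7 says "Hold next dose until grade 1 or baseline and resume flavopiridol if further therapy is indicated" at grade 3 or above, which could pass for a general grade 3 hold rule. It is limited to easily replaced abnormalities without serious consequences, such as low phosphorus, so it proves nothing about diarrhea.
- A reader might see a second safety conflict in tumor lysis syndrome (TLS) prophylaxis. Section 3.2.1 has 6 hours of saline (0.2 L/h × 6 h = 1.2 L) and 5 days of allopurinol. Section 3.3.6 items 4–5 have at least 10 hours of dextrose-bicarbonate before the dose (0.2 × 10 = 2.0 L) and allopurinol for at least a week. But the shorter text appears only under Phase 1 dosing and defers to the detailed guidelines, and section 3.3.6 allows individual modification. What remains is mainly a stale pointer: section 4.3 is now Neutropenia.

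One could also conform the narrative to the table. That is a clinical choice, but it would leave dosing permitted during active grade 3 or dehydrating diarrhea.

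**Conclusion.** The inconsistency is real and should be corrected. For a patient with grade 3 diarrhea on the dose day, section 3.3.2 supports either 0 mg/m² or 64–80 mg/m². For grade 1–2 diarrhea with mucus or dehydration it supports either 0 or 80–100 mg/m². These sizes assume that the condition is present when the dose is due and that the 20% cut is a first reduction from the planned weeks 2–4 dose.

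The point concerns patient safety and uniform dosing. A reader might infer that it undermines the DLT count or the phase II operating characteristics. The documents do not support that: the DLT definition and the Simon boundaries are the same under either rule. The TLS text is a minor editorial matter.

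**What to change.** Replace the within-cycle diarrhea table with the following rows. The clinical team should confirm the restart terms, because the narrative gives none and they are adapted from the grade 4 row.

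| Diarrhea in the previous week | Flavopiridol |
|---|---|
| Below grade 3, no mucus or dehydration | No change |
| Below grade 3, with mucus or dehydration | Hold and hydrate until mucus and dehydration have resolved |
| Grade 3 | Hold and hydrate until below grade 3 and any mucus or dehydration has resolved, then reduce by 20% |
| Grade 4 | As now, with restart also requiring that any mucus or dehydration has resolved |

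The grade 3 row replaces the clause on persistence beyond 7 days. If that clause was meant for residual diarrhea below grade 3, the team should say so and restate it separately. The same amendment could usefully state the base of the 20% cut and whether a held weekly dose is skipped or made up.

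Editorial: in section 3.2.1, replace the saline and allopurinol sentences with a reference to section 3.3.6 items 4–5. Change the TLS pointers to 4.3 (sections 3.2.1 and 4.1) and to 4.3.6 (section 3.3.6 item 19 and study calendar note H) to 3.3.6.

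Cost: a protocol amendment, with no change to sample size, dose levels or DLT definition. A few weekly doses may be withheld that the table alone would have given, and the narrative already says to hold all of them.
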